# TABLE 2: SCHEDULE OF STUDY TREATMENT PROCEDURES

Intervention group,	Comparison group,
10 weekly coaching offered over 12 weeks	
Session #1 in-person on day of baseline assessment visit 2	1 educational session (15-30 min.) offered in-person on
Sessions #2-10 offered in-person or via phone/video	day of baseline assessment visit 2
Monthly booster calls from 12-24 weeks	Monthly calls to retain contact from weeks 3-30

#### 2 BACKGROUND INFORMATION AND RATIONALE

### **OVERVIEW**

This protocol is for the third and final part of a set of studies with an overall goal to develop and pilot test the Diabetes Homeless Medication Support (D-Homes) program. D-Homes is a collaborative care intervention using motivational interviewing and behavioral activation alongside education and psychosocial support to improve medication adherence tailored to the experiences of people experiencing homelessness and diabetes (DH). Our team's central hypothesis is that medication adherence and diabetes self-care (and eventual glycemic control, health care use/cost) will improve with an intervention tailored to the unique context of DH.

This work builds upon part 1 (HSR#19-4622) during which we completed Aim 1 activities to develop the initial Diabetes Homeless Medication Support (D-Homes) treatment manual through focus groups with DH at various levels of glycemic control and interviews with their multi-disciplinary providers. Data from this phase has identified barriers and strategies for medication adherence, patient values regarding medication, and treatment preferences and informed development of part 2 (HSR #20-4863). Part 2 was a single arm treatment development trial that tested the feasibility and acceptability of study procedures and refined the D-Homes treatment manual through test cases (n=10-15). We found the D-Homes manual and study procedures are feasible and acceptable to DH as measured by self-report and post-treatment interview but that treatment engagement lessened for participants with the highest degrees of housing instability.

This protocol describes part 3, a fully randomized pilot study in concordance with study Aim 3.

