### 4.2 Allocation to Groups and Blinding

Participants will be randomized to either the intervention or a control group (1:1). Randomization will be stratified by housing type (unstable (e.g., shelter, staying outside) vs.

more stable (e.g., worry about rent payment, supportive or transitional housing)). Randomization will occur after baseline assessment visit #2 via REDCap. Staff who conduct who conduct the follow-up assessment visits will be blind to condition.

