# 4.3.2 Total Number of Study Sites/Total Number of Subjects Projected

Enrollment for the study will continue until 54 participants have been enrolled.

HHRI will serve as the only site for this study.

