#### 7 STATISTICAL CONSIDERATIONS

# 7.1 Primary Endpoint

The primary endpoint of this study is the satisfaction of participants in this pilot randomized trial (via CSQ-8).

The feasibility and acceptability of study protocols for recruitment, retention, and randomization are also important. We will assess this by measuring our ability to recruit and retain participants, and the assessment and treatment visits we can deliver (i.e., participant's attendance and follow-up with scheduled sessions and treatment activities). In addition to above outcomes, we will carefully track the number and types of between-treatment communications with participants (who initiated communication; form of communication: text, calls, e-mails, etc.).

We will consider the study feasible if we enroll 75% of those screened who meet inclusion criteria, and 75% of enrolled participants complete at least one follow-up. We will consider 50% session attendance as indicative of feasibility. We will consider the intervention acceptable if 70% of participants are satisfied and would recommend it to others.

We will also analyze our primary clinical endpoint of change in A1c between intervention and comparison groups between baseline follow-up visit #1 (approx. 12-16 weeks)

if it changes from baseline to between intervention.

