### 9 STUDY ADMINISTRATION

## 9.1 Treatment Assignment Methods

- **9.1.1 Randomization or Other Assignment** Randomization will occur at the 2nd baseline visit, and will be done using a pre-generated randomization schedule in REDCap. Randomization will be stratified into 2 strata based on severity of housing instability: "unstable" (e.g., living in shelter, staying outside) and "more stable" (e.g., history of homelessness that's now resolved, worry about rent payment, subsidized housing).
- **9.1.2 Blinding** Staff who conduct the follow-up assessment visits will be blind to condition.
- **9.1.3 Unblinding** Multiple staff members will be trained in how to complete the outcome assessments. In the event that a staff member is unblinded during the first follow-up assessment visit, a different blinded assessor will complete the 24-week visit.

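### The feasibility and acceptability thresholds are judged only on pooled percentages, so an overall pass can mask weak retention or attendance in the unstably housed stratum

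*Combined protocol and SAP*

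**What the plan says.** The Overview in section 2 reports that Part 2, a single-arm study planned for 10 to 15 test cases, found the manual and procedures feasible and acceptable, but that "treatment engagement lessened for participants with the highest degrees of housing instability". No rate is given.

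Section 9.1.1 carries that factor into the design: "Randomization will be stratified into 2 strata based on severity of housing instability". Section 4.2 says the same and sets 1:1 allocation. Neither section gives a quota or an expected size for either stratum. Section 4.3.2 fixes only the total: "Enrollment for the study will continue until 54 participants have been enrolled".

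Section 7.1 sets the criteria as overall percentages:
- Enrolment: "We will consider the study feasible if we enroll 75% of those screened who meet inclusion criteria".
- Retention: "75% of enrolled participants complete at least one follow-up".
- Attendance: "We will consider 50% session attendance as indicative of feasibility".
- Acceptability: 70% satisfied and willing to recommend the programme.

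The synopsis (Statistical and Analytic Plan) also states pooled percentages, but sets attendance at 70%, not 50%, and words the retention criterion as completing follow-up.

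Section 7.4.1 compares CSQ-8 satisfaction scores by arm and by race/ethnicity, and describes the highest and lowest quintiles by age, gender and race/ethnicity. Housing appears there only as an adjustment in the outcome models, and in 7.2 as an exploratory outcome. Retention, attendance and satisfaction by housing stratum are not planned anywhere.

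**The concern.** The sponsor already has a signal that engagement varies with housing, and it judged that factor important enough to stratify on. Eligibility (section 4.5.1) runs from people staying outside or in shelter to people in supported housing or worried about rent. Across so wide a range, a pooled percentage mixes two groups in proportions that the protocol does not control. Stratified randomisation balances the arms within each stratum, but does not fix how many unstably housed people are recruited.

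Section 3.1 says this pilot is to support a later, fully powered study. If a pooled pass conceals poor retention or attendance among the least stably housed, that study's retention assumptions, eligibility and delivery plan would rest on a rate that does not apply to part of its population. Part 2 itself had this pattern: feasible overall, with weaker engagement in one subgroup. The Part 3 criteria as written cannot show whether it recurs.

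**Working it through.** The plan gives no calculation behind 54 (section 7.5), so there is no figure to reproduce. The check asks how low the unstable stratum can fall while the pooled threshold is still met.

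**Inputs from the documents.** N = 54 (4.3.2); 1:1 allocation, so about 27 per arm (4.2); retention threshold 75% (7.1); attendance threshold 50% (7.1) or 70% (synopsis).

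**Assumptions, because the documents give no figures.** All 54 enrolled are randomised. The unstable share is one quarter, one third, one half or two thirds, that is n_u = 14, 18, 27 or 36. Stratum rates are as shown below.

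**Retention count.** 0.75 × 54 = 40.5, so 41 must be retained. 41/54 = 75.9%, exact 95% interval 62-87%.

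**Stable-stratum retention needed for a pooled pass**, given unstable retention r_u: (41 − n_u × r_u) / (54 − n_u).

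| n_u | r_u = 40% | r_u = 50% | r_u = 60% |
|---|---|---|---|
| 14 | 35.4/40 = 88.5% | 34/40 = 85.0% | 32.6/40 = 81.5% |
| 18 | 33.8/36 = 93.9% | 32/36 = 88.9% | 30.2/36 = 83.9% |
| 27 | 30.2/27, impossible | 27.5/27, impossible | 24.8/27 = 91.9% |
| 36 | impossible | impossible | 19.4/18, impossible |

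With 14 to 18 unstably housed, stable retention of 82-94% is therefore enough. In whole people, 9/18 (50%) plus 32/36 (89%) gives 41/54, a pass.

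**Lowest unstable retention compatible with a pass when the stable stratum retains about 90%:**
- one quarter unstable: 36/40 stable leaves 5/14 (36%)
- one third: 32/36 leaves 9/18 (50%)
- one half: 24/27 leaves 17/27 (63%)
- two thirds: 16/18 leaves 25/36 (69%)

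**How often this would happen.** Take true retention as 60% unstable and 90% stable, with independent binomials. The probability that the pooled threshold is met while the unstable stratum is observed below 75% is 0.80, 0.74, 0.47 and 0.16 for shares of one quarter, one third, one half and two thirds.

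**Attendance (about 27 in the intervention arm, read as mean attendance).** Required unstable mean = (threshold × 27 − stable mean × n_s) / n_u.
- 50% threshold, stable mean 70%: one third unstable, (13.5 − 12.6)/9 = 10%; one half, (13.5 − 9.1)/14 = 31%; two thirds, (13.5 − 6.3)/18 = 40%.
- 70% threshold, stable mean 80%: one third, (18.9 − 14.4)/9 = 50%; one half, (18.9 − 10.4)/14 = 61%; two thirds, (18.9 − 7.2)/18 = 65%.

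**Precision within strata.** Exact 95% intervals: 10/14, 42-92%; 14/18, 52-94%; 9/18, 26-74%. A quarter to a third of 27 is only 7 to 9 people in the intervention arm; 5/9 gives 21-86%.

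**A hard 75% rule inside the unstable stratum.** If true retention there is 80%, the observed rate reaches 75% with probability 0.70, 0.72 and 0.71 for n = 14, 18 and 27, so the rule would wrongly fail about 3 times in 10.

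**The case against.** **The mix is unknown and may be unfavourable to the concern.** Recruitment draws on shelters, drop-in centres and homeless health clinics (4.1.1, 9.5), so the unstable share could be half or more. At 27 unstable, 40% or 50% retention there cannot pass, and at 36 even 60% cannot, so the pooled threshold would catch the failure. This stands, and is why the size is stated by share.

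**A reader might infer that the study could be declared feasible with only the more stable stratum retained.** The arithmetic rules this out at the assumed shares: all 40 stable and none of 14 unstable gives 40/54 = 74.1%, and all 36 stable with none of 18 gives 66.7%. Both fail. The risk is weaker performance hidden, not absence hidden.

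**A reader might also infer that the pooled rate is driven mainly by the recruited mix.** That needs a large gap between strata, and no rates are given. With 70% against 80% retention, moving from 14 to 36 unstable shifts the pooled rate only from 41.8/54 = 77% to 39.6/54 = 73%.

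**The Part 2 signal is narrow.** It comes from a very small single-arm study and concerns treatment engagement. Lower retention or satisfaction was not reported. This stands; attendance is the criterion closest to the signal, and retention is an extension of it.

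**The unstable stratum is not the whole target.** Section 4.5.1 also admits people in supported housing or worried about rent, so a pooled criterion matches the stated population. This stands as to the target, but does not remove the value of the split.

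**Housing is partly handled already.** It is stratified on, recorded at baseline and both follow-ups (Table 1), and adjusted for in the models (7.4.1). Section 4.1.3 gives particular attention to people who end sessions early. None of this yields retention, attendance or satisfaction by stratum.

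**Conclusion.** The point holds as a gap in pre-specified reporting. The thresholds in 7.1 are pooled, although the sponsor's own earlier result and its stratification factor both point to housing. If a quarter to a third of participants are unstably housed, a retention pass is compatible with about 40-60% retained in that stratum when 82-94% of the other is retained. The masking shrinks at one half and is slight at two thirds. Under the 50% attendance threshold the room for masking is wider. All of these figures rest on assumed stratum shares and rates.

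The pilot is not invalid, and the documents do not support a separate feasible/not-feasible conclusion for the unstable stratum: at 14 to 27 people a strict rule is unreliable, and attendance there may rest on 7 to 9 people. What is supportable is estimation by stratum, used to qualify the overall statement. Even wide intervals can inform: 9/18 has an upper limit of 74%, below the 75% threshold.

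**What to change.** First reconcile two inconsistencies on which the table depends:
- The attendance threshold is 50% in 7.1 and in the synopsis rationale, but 70% in the synopsis statistical plan. State one figure, and how attendance is computed. The two wordings of the retention criterion (7.1 and synopsis) should be aligned at the same time.
- The examples of more stable housing differ between 4.2 and 9.1.1; only 9.1.1 lists homelessness that has since resolved. Give one stratum definition.

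Then add to 7.1 that:
- retention, session attendance (intervention arm only) and satisfaction will also be reported by the two randomisation strata, with stratum sizes and exact 95% intervals for proportions;
- the overall feasibility statement will be qualified by the unstable-stratum estimate and its interval;
- no separate pass/fail threshold applies within a stratum.

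The cost is one extra table from data already collected. Its intervals will be wide (14/18: 52-94%), and the text should say so. Specifying it now matters because a split chosen after the pooled result is known would carry less weight.

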### **SIGNFICANCE**

Homeless people in the US face disproportionate risk for premature death in part due to poorly controlled chronic diseases including diabetes. One and a half million unique US adults access homeless shelters annually. However, the total number of people experiencing homelessness (Box) is likely much higher with an estimated 7 million additional people living "doubled up" with family/friends in 2014. New data recently established that 44% of all adults, and 37% of adults with diabetes, at US community health

centers experience unstable housing. All-cause mortality rates among people experiencing homelessness in the U.S. are 4.5 to 9.6-times higher than the general population. Premature death often results from preventable chronic diseases including diabetes (2%) and its related comorbidities,

**Box.** Defining Homelessness:

Many definitions of homelessness exist. We adopt that of the U.S. government which includes people who:

- · Lack "fixed, regular, adequate nighttime residence"
- Stay at emergency shelters, temporary living facilities, other places not meant for human habitation
  - Will imminently lose their primary residence
    (HEARTH Act, 2011)

e.g. heart disease (16%). While diabetes *prevalence* among the homeless and general population is comparable (≈8% in both), there is evidence indicating large disparities in diabetes *outcomes*. Patients with type 2 Diabetes who are Homeless, herein abbreviated DH, have worse glycemic control and are hospitalized for diabetes-related complications a decade earlier than their housed peers. New data finds unstably housed adults have over five times the odds of diabetes-related emergency or hospital visit. This is of particular concern given "metabolic memory," **or long-term vascular stresses which persist after** 

significant early hyperglycemia despite later glucose normalization. While homelessness and unstable housing are increasingly recognized for their impact on diabetes control, including by the American Diabetes Association, there is a paucity of solution-driven research. Thus, there is an urgent need to develop novel treatments to improve glycemic control in DH as they move across the spectrum of unstable housing.

Medication adherence is a complex behavior critically linked to improved overall and diabetes-specific outcomes. The rate of adherence for all long-term therapies averages 50% in the general (non-homeless) U.S. population due to barriers at various levels including: (i) patient, (ii) medication/disease, (iii) system, and (iv) socioeconomic. Among privately insured populations, non-adherence to diabetes and related cardiovascular medications is associated with poor disease control (e.g., higher hemoglobin A1c and blood pressure), as well as increased risk of all-cause mortality and visits to the hospital and emergency department, and total health care costs. In low-income populations, cost-related non-adherence is common, and non-adherence is correlated with poor glycemic control. In fact, every 10% improvement in diabetes medication adherence reduced hemoglobin A1c by 0.16%. The importance of medication adherence is recognized by NIH with an active FOA to improve medication adherence (PA-18-722).

Poor diabetes outcomes among the homeless is caused by low medication adherence. Non-adherence to medications across disease types is a known concern for homeless people especially when they are young (age <40 yrs.), have comorbid mental health/substance use disorders, experience food insecurity and frequent the emergency department. Despite high rates of overlapping physical and behavioral co-morbidities, 36% of US homeless adults report unmet needs for prescription medications. Small studies find lower medication adherence in homeless patients when directly compared to housed peers. DH patients specifically report challenges obtaining, storing, and retaining medication (especially insulin), and stigma surrounding the possession/use of needles.

[figure not shown]
Existing evidence-based models targeting medication adherence to improve diabetes will be the starting point for our novel intervention. We will draw from such interventions which target patient and system-level factors to improve diabetes self-care activities, including medication adherence, for historically disadvantaged groups. The overarching theoretical model guiding treatment development is the **Information** Motivation Behavioral Skills model. Our proposed treatment is also consistent with the Collaborative Care Model, a care management approach designed for individuals with multiple chronic conditions with known success improving diabetes outcomes in patients with depression. 45,46 The Collaborative Care Model frequently uses Motivational Interviewing as the counseling approach, as we plan to in this study. **Behavioral Activation (BA)** is another counseling approach that complements motivational interviewing. Behavioral intervention is empirically supported to address medication adherence in a population with high levels of underlying psychiatric disease (especially depression) and/or psychosocial stress. 96-99 BA is easier to train than other empiricallysupported counseling treatments and can be delivered with fidelity by bachelor's level practitioners. 100-101 BA is appropriately complemented by motivational interviewing, a person-centered, evidence-based approach to behavior change focused on participants' values and preferences and overcoming expected ambivalence to change. 48 It is particularly appealing to groups with historic disadvantage and minority race, 48 including the

homeless, and has improved medication adherence in non-homeless people with diabetes including when delivered by trained, non-mental health professionals to low-income populations. We will use BA first and employ MI when participants demonstrate ambivalence to change.

We will also integrate education using content consistent with the latest diabetes care guidelines. And we will offer problem-solving to address psychosocial needs (including food and housing) modeled after clinic-based approaches for homeless veterans. These evidence-based interventions offer a starting point for a new intervention which will be tailored to the unique context of DH through the iterative, multi-stakeholder process described below.

# 2.1 Name and Description of Intervention

The behavioral intervention tested in this protocol is the Diabetes-HOmEless Medication Support (D-HOMES) program. This will be a 12-week in-person, video, and/or phone-based support program centered on providing diabetes education, motivational and goal-setting support, and resource and care coordination (Figure 2). Psychological approaches of behavioral activation and motivational interviewing will be used along with provision of educational materials and tools to support behavior change, see Section 3. for details.

## 2.2 Selection of Treatment Dosages

Treatment doses are similar to a multiple health behavior change intervention currently underway by [name] ("Development of an Integrated Depression and Behavioral Risk Factor Reduction Intervention for Secondary Prevention following Acute Coronary Syndrome," 1R03HL136540), primary mentor on this study. This is also in line with current literature about behavioral interventions to support improved diabetes self-management via medication adherence and psychosocial wellness.  During this treatment development phase we will monitor and adjust the number and duration of planned sessions based on the data from case study participants. This will inform Aim 3 randomized pilot future steps.

# **2.3** Relevant References See Section 10 for References.

# 2.4 Compliance Statement

This study will be conducted in full accordance of all applicable Hennepin Healthcare Research Policies and Procedures and all applicable Federal and State laws and regulations. All episodes of noncompliance will be documented and reported according to the Prompt Reporting Guidelines, Attachment EEE, of the Hennepin Healthcare IRB Policies and Procedures.

The investigators will perform the study in accordance with this protocol, will obtain informed consent and will report unanticipated problems involving risks to subjects or others and SAEs in accordance with The Hennepin Healthcare IRB Policies and Procedures and all Federal requirements. Collection, recording, and reporting of data will be accurate and will ensure the privacy, health, and welfare of research subjects during and after the study.

### 3 STUDY OBJECTIVES

The purpose of the study is to pilot test a collaborative care intervention using motivational interviewing and behavioral activation alongside education and psychosocial support to improve medication adherence tailored to the experiences of people experiencing homelessness and diabetes (DH).

# 3.1 Primary Objective (or Aim)

The primary objective of this study is to conduct a randomized pilot trial of the D-Homes intervention. This will support our ultimate goal to determine the efficacy of this 10-session behavioral activation and motivational interviewing support program for DH in a future, fully-powered study. The outcomes we will use to assess this pilot phase of our work will be participant satisfaction, our ability to recruit and retain participants, the acceptability and process of the comparison group, and follow-up until a 24-week final assessment visit.

